3. Role in research	Post-doctoral researcher, neuroimaging support	
4. Training in research ethics and/or research integrity Research integrity training within the past 3 years is compulsory for all University research staff and students. Please enter date of relevant course completion (one of 1a, 1b or 1c must be completed).	Course Title	Date completed
	1a. Research Integrity Core Course (New researchers & students)	N/A
	1b. Research Integrity Refresher Course (Experienced researchers)	March 2022
	1c. Other (e.g. GCP - please specify title)	Human Tissue Act training - 02/02/2022 Human Tissue Act training (MRC) - 23/05/2022
	2. Supplementary Module – Research involving human participants	

	
cortico-striatal, and hippocampal areas).
 
2) To investigate the effects of single-dose pitolisant on behavioural cognitive performance in tasks of verbal and visual working memory (Instrumental n-back, Change Detection Task), social cue processing (Facial Emotional Recognition Task), sensitivity to reward and loss (Probabilistic Instrumental Learning Task) and emotional/non-emotional response inhibition (Emotional Go/No-Go Task)
 
3) To investigate the effect of single-dose pitolisant on subjective cognition (PDQ).
	
cortico-striatal and hippocampal regions (fMRI BOLD signal)
 
2. Change in performance (accuracy/response time) on emotional go/no-go task
 
3. Change in performance during the Probabilistic Instrumental Learning Task
 
4. Change in performance (accuracy/response time) during Instrumental n-back task
 
5. Change in performance in the Change Detection Task
 
6. Change in performance (accuracy/response time) during Facial Emotional Recognition Task
 
7. Changes in measures of subjective cognition (Perceived Deficits Questionnaire [PDQ])

8. Name of drug/substance	Pitolisant (Brand name: Wakix)	
9. Purpose of drug/substance use in this research	
Cognitive and affective processing are underpinned by monoaminergic neurotransmission and neurosteroid systems, yet there are many aspects of these systems that remain unknown in humans. In particular, monoaminergic histamine 3 (H3) receptors are abundant in CNS regions underpinning cognitive processing (prefrontal cortex, hippocampus, and striatum), yet their role in humans remains unclear. Evidence from animal models suggests H3R antagonism improves cognitive functioning, however these specific effects are yet to be examined in humans. Similarly, the function of sigma-1 (σ-1) receptors in the brain is not well understood in humans despite strong evidence of pro-cognitive effects in animal models.
 
We will investigate the effect of pitolisant, a dual H3R antagonist and σ-1R agonist, on cognitive and affective processing, in addition to changes in functional connectivity. We will measure these effects through a battery of neuropsychological tasks (e.g., Affective Go/No-Go Task; Instrumental dual n-back task), self-rated measures of cognitive function (PDQ), and resting state fMRI and fMRI data acquisition during the verbal n-back and memory encoding tasks.
	
10. Adverse reactions and side effects posing a particular risk with this drug/substance	
Pitolisant is approved for use and licensed in the US (FDA – 2019 ), EU and UK (EMA – 2016 ) for treatment of narcolepsy. Safety and tolerability data from clinical studies of pitolisant in narcolepsy of up to 8 weeks administration reveal its most common adverse effects are nausea (6%), insomnia (6%), and anxiety
	

	
(5%). Most relevant to this protocol is its tolerability profile in a single dose (40mg) in healthy volunteers, where 1 in 6 participants experienced increased sleep duration, dystonia and dizziness. A recent study in healthy volunteers showed no cardiac safety signals in individuals taking up to the maximum dose of pitolisant (36mg/day).
 
In this study, we will use a single dose of 36mg pitolisant within its recommended dose range (4.5–36 mg/day). Study participants will be screened to exclude those presenting with QT prolongation via ECG assessment as cautioned by the FDA, in addition to cautions contraindications for those with gastrointestinal disorders, epilepsy, mental health difficulties, clinical eating disorders and severe obesity by NICE.

--	---

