### **Screening visit:**

Participants who met the eligibility criteria during the online screening then would be invited to book themselves into a screening visit occurring at the Neurosciences Building, Warneford Hospital Site. The visit will take approximately 60-90 minutes to complete. A physical copy of informed consent will be taken at the start of visit as the consent obtained during the online screening would have been done remotely. The screening visit involves the following procedures:

- Personal contact details collection (paper)
- Weight, height measurement
- Vital signs assessment (blood pressure and ECG to check for heart electrical abnormalities)
- 12 lead ECG
- Urine drug screening
- Urine pregnancy test
- Digital Span Task – Forward/Backwards (to assess baseline cognitive ability for randomisation procedure); this task will require participants to repeat a sequence of numbers in a particular order (forwards or backwards) orally to the researcher.
- SCID-V Interview (Structured clinical Interview for DSM-V, a set of standard clinical questions asking about current and past psychiatric illness)
- MRI screening form

All physical health assessments will be overseen by the medical officer attached to this study ([name]) or other delegated medical professional. For the ECG assessment, a chaperone will be offered to participants according to the risk assessment. All clinical procedures in this study (including COVID-related restrictions) will be carried out following a study-specific risk assessment and in adherence to the standard operating procedure of Neurosciences Building risk assessment (see APPENDIX C - NEUROSCIENCES BLDG RISK ASSESSMENT). If participants fit the study criteria they will then be invited for the second visit: 'Study visit'. A maximum of four weeks is allowed between the Screening Visit and the Study Visit. If this duration is exceeded, another screening will be performed to ensure eligibility.

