## **2. Subsequent Visits**

### Study Visit

Participants who are medically approved to take part in the study after the screening visit are invited to take part in the study visit. Prior to the study visit, and after the screening visit, participants will be randomised using the variance minimisation algorithm described above to ensure a balance of covariates of interest across treatment and placebo groups. The randomisation code will be drawn up by a researcher not involved in the study using an randomisation procedure known as variance minimisation, following a procedure outlined by Sella, Raz & Cohen Kadosh (2021). Participants will be allocated to placebo or treatment groups based on gender, level of education, and their digit span score (as an index of general intelligence). Allocation of treatments will be recorded on a Randomisation List which will be updated when each new participant enters the randomised phase. The Randomisation List will be held securely within the Neurosciences Building by the study medic ([name]). Pitolisant and placebo agents will be kept securely within a locked medicines cabinet also within the Neurosciences building.

During the visit, participants will receive either a single dose of pitolisant (36mg single dose) or placebo. They will receive the dose at the Neurosciences Building, Warneford Hospital site. The study has a double-blind design thus neither the researchers nor the participant will know whether pitolisant or placebo is given. On arrival, participants will briefly be reviewed to ensure the inclusion criteria are still satisfied. Prior to drug or placebo administration, the following procedures will be undertaken:

- Inclusion/exclusion criteria review

- Completion of the MRI screening form (APPENDIX H - 3T VOLUNTEER SCREENING FORM) once more to ensure it is still safe for them to undergo fMRI scanning.
- Clinical screening, mood and side effects questionnaires (to establish baseline) on qualtrics – PHQ-9, GAD-7, PANAS, PDQ and Need for Cognition Scale

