- Affect, Mood, Subjective Cognition and Side Effects questionnaires (for end-point):
  - PHQ-9
  - GAD-7
  - Visual Analogue Scale
  - Perceived Deficits Questionnaire
  - Side Effects Questionnaire
  - PANAS
  - Need for Cognition Scale
- Instrumental *n*-back task – this widely used task will be done after scanning is complete; it will require participants to complete a version of the *n*-back task in the scanner, but this time participants are rewarded or punished for performance. Participants will start with £1.00 and can earn up to £10 based on performance (similar to the PILT), but cannot lose less than £0.00. This task will involve more complex levels of working memory processing (including 4-back, 5-back).
- A change detection task – a short task of visual working memory which requires participants to view an array of ‘items’ (e.g. coloured blocks) for a short period of time, and after a short period they are shown the same array once again with one subtle change (e.g., one colour has been changed). Participants must identify the change.

- Emotional Go/No-Go task (EGNG) -- this task follows a 'go/no-go' format where participants will be presented stimuli on-screen which they are instructed to either press a button for 'go' trials or inhibit their response. Emotional and non-emotional distractors will be used to check the effect of emotional distraction on response inhibition.
- Facial Emotional Recognition Task (FERT) – the widely-used task will ask participants to recognise the emotion of faces displayed on the screen in sequence; emotions include: sad, surprised, angry, disgusted, happy, neutral).

Once participants had completed these procedures then the study visit will end. Before leaving, participants will be given a wallet-sized card with key details about the study and contact information of a member of the study team to contact if they have any questions. The card will also include the phone number of the out-of-hours BRC on-call medic service in case they need medical advice related to the study out of standard office hours. At the end of this visit, participants will be advised not to drive, cycle or operate machinery, in case they experience any side effects from the drug. To ensure participants get home safely after the visit, the researcher will either arrange a taxi or travel expenses (e.g. bus tickets) for the journey will be reimbursed.

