#### 4. Analysis of Outcome Measures

R Software will be used to analyse all psychometric, cognitive and neuroimaging data. Sample characteristic data (e.g. age, gender, and years in education) will be analysed using an appropriate analysis of variance (e.g. t-test or Mann-Whitney U), depending on model assumptions being satisfied. Cognitive and neuroimaging data will be analysed using a between-groups ANOVA approach, with appropriate normality transformations and Greenhouse–Geisser correct where the distribution and/or degrees of freedom does not meet model assumptions. Post-hoc analyses will be corrected using Bonferroni (or Bonferroni-Holm) correction. Analysis of fMRI endpoints will be completed using the FSL software package.

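### Five task outcomes are defined as change, but each task is run only once, after dosing; they should be redefined as post-dose scores

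*Protocol*

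**What the plan says.** The objectives and outcome measures table lists outcome 2 as "Change in performance (accuracy/response time) on emotional go/no-go task", outcome 3 as "Change in performance during the Probabilistic Instrumental Learning Task", outcome 4 as "Change in performance (accuracy/response time) during Instrumental n-back task" and outcome 5 as "Change in performance in the Change Detection Task". Outcome 6 (FERT accuracy and response time) and outcome 7 (PDQ) are also worded as change. The primary outcome and the start of outcome 1 cannot be read in the text at hand and are not judged here.

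On timing, Section G.1 (Screening visit) has one cognitive task, a digit span, given "to assess baseline cognitive ability for randomisation procedure". Before the dose, Section G.2 (Study Visit) lists eligibility and MRI safety checks and "Clinical screening, mood and side effects questionnaires (to establish baseline) on qualtrics"; PDQ is among these questionnaires. All five outcome tasks come after the dose. Of the instrumental n-back the protocol says "this widely used task will be done after scanning is complete".

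On analysis, Section J.4 says "Cognitive and neuroimaging data will be analysed using a between-groups ANOVA approach". It names no covariate. It mentions psychometric data only as something to be analysed in R.

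**The concern.** A change outcome needs two measurements on the same person, or at least a pre-dose value. If the five tasks have no pre-dose value, their definitions cannot be followed as written. Someone must then decide later what the outcome really is: the post-dose score, a contrast within the task, or a difference from some other measure. An outcome definition should not leave that choice open until the data are in.

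There is a related question of efficiency. Allocation is balanced on digit span, gender and level of education, and PDQ has a true baseline. The protocol does not say that the analysis uses any of these as covariates.

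**Working it through.** **Step 1. Outcome wording against schedule.**

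| Outcome | Task | Before dose | After dose |
|---|---|---|---|
| 2 | Emotional Go/No-Go | none | once, after the scan |
| 3 | PILT | none | once, in the scan, after the two-hour wait |
| 4 | Instrumental n-back | none | once, after the scan |
| 5 | Change Detection | none | once, after the scan |
| 6 | FERT | none | once, after the scan |
| 7 | PDQ | yes, at the study visit | yes, at end-point |

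Nothing else in the schedule can serve as a baseline for outcomes 2 to 6. Digit span is a different task. The verbal n-back in the scanner is also post-dose. The next-day follow-up has a questionnaire and no task. Each participant receives one dose in one period, so there is no second period to compare with.

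**Step 2. Does the sample size assume change or a post-dose score?** Inputs from Section J.3: one-way ANOVA, effect size 0.4, alpha 0.05, power 80%, total 52, plus 4 to give 56 (28 per group). Take k = 2 groups and read 0.4 as Cohen's f, so d = 2f = 0.8. The noncentrality is λ = N·f², with 1 and N − 2 degrees of freedom.

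- N = 50: λ = 50 × 0.16 = 8.00, power 0.792
- N = 52: λ = 52 × 0.16 = 8.32, power 0.807
- N = 56: λ = 56 × 0.16 = 8.96, power 0.836

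The stated 52 reproduces. The calculation contains no pre-post correlation, so it fits a single post-dose score per person. Redefining outcomes 2 to 6 that way leaves N unchanged.

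**Step 3. PDQ: what a stated baseline adjustment could be worth.** Let r be the pre-post correlation and assume equal pre and post SDs. Relative to the post-dose score alone, the error variance is 2(1 − r) for a change score and 1 − r² for ANCOVA. ANCOVA is never worse than change, since 2(1 − r) − (1 − r²) = (1 − r)² ≥ 0. It is never worse than post-only, since 1 − r² ≤ 1. The price is one degree of freedom.

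At N = 56, f² = 0.16 is divided by the relative variance:

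| r (assumed) | Post-only | Change: λ, power | ANCOVA: λ, power |
|---|---|---|---|
| 0.3 | 0.836 | 8.96/1.40 = 6.40, 0.700 | 8.96/0.91 = 9.85, 0.869 |
| 0.5 | 0.836 | 8.96/1.00 = 8.96, 0.836 | 8.96/0.75 = 11.95, 0.924 |
| 0.7 | 0.836 | 8.96/0.60 = 14.93, 0.967 | 8.96/0.51 = 17.57, 0.984 |

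The protocol gives neither r nor an effect size for PDQ. The d of 0.8 is borrowed from the sample size calculation, which cites n-back accuracy and BOLD results.

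**The case against.** The strongest reply is that change is used loosely here to mean a drug effect. The adjacent objective speaks of the effect of a single dose on performance, the design is parallel-group, and both the ANOVA and the sample size point to a drug-placebo difference after dosing. This is probably what was intended, and it stands as far as analysability goes. It does not rescue the wording: the outcome definitions still contradict the schedule, and an SAP cannot create data that are not collected.

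Four stronger readings are tempting, but the protocol does not support them.

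- A reader might infer that the five outcomes are lost. They are not: post-dose scores exist and N is adequate for the assumed effect.
- A reader might infer that PDQ is to be analysed without its baseline. The ANOVA sentence covers cognitive and neuroimaging data and fixes no specific PDQ model. A change score would use the baseline, and the mention of Greenhouse–Geisser leaves a within-person term possible.
- A reader might infer that digit span is discarded. It is used in the minimisation, which is its stated purpose.
- A reader might infer that the registry carries the same error. Section O only says that the study will be preregistered; no entry is at hand.

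It is also fair to say that covariates are often left to an SAP. Their absence is therefore not counted as an error here, only as something worth settling when the outcomes are reworded.

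**Conclusion.** The contradiction is real and confined to definition. Five of the seven visible numbered outcomes cannot be computed as worded, because each task has only a post-dose measurement. This rests on the outcome table and the visit schedule alone and needs no assumption. The sample size is not affected: 52 reproduces, and 56 gives 83.6% power at f = 0.4.

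Adjustment for the minimisation factors and for pre-dose PDQ is an improvement on what is stated, not the correction of a stated mistake. For PDQ, ANCOVA is at least as efficient as either alternative apart from the one degree of freedom. A raw change score has less power than the post-dose score alone only when r is below 0.5. At r = 0.7 the gain of ANCOVA over change is under two percentage points. The power figures are illustrative and depend on assumed values of r and d. No gain is quoted for the task outcomes, because the protocol gives no correlation between the allocation factors and the task scores.

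**What to change.** - Redefine outcomes 2 to 6 as the post-dose score on each task, compared as pitolisant minus placebo. Keep N at 56.
- State in Section J.4 that the task models include digit span, gender and level of education as covariates, since allocation is balanced on all three. Leaving out a balanced factor that predicts the score keeps its variance in the error term.
- State the PDQ analysis as the end-point score with the pre-dose PDQ score as covariate.

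The cost is outcome wording and a few degrees of freedom. All the data are already scheduled to be collected; no visit, task or participant is added. The change should be made before unblinding.

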## Section D. Abbreviations

Define all unusual or 'technical' terms related to the research. Add or delete rows as appropriate. Maintain alphabetical order for ease of reference.

BMI	Body Mass Index
BOLD	Blood-Oxygen Level Dependent
BRC	Biomedical Research Centre
CNS	Central Nervous System
CUREC	Central University Research Ethics Committee
DHEA	Dehydroepiandrosterone
DSM-V	The Diagnostic and Statistical Manual of Mental Disorders, Fifth Edition
ECG	Electrocardiogram
EGNG	Emotional Go/No-Go Task
EMA	European Medicines Agency
FDA	Food and Drug Administration
FERT	Facial Emotional Recognition Task
fMRI	Functional Magnetic Resonance Imaging
FMRIB	Oxford Centre for Functional MRI of the Brain
GAD-7	Generalised Anxiety Disorder Assessment
GCP	Good Clinical Practice
GP	General Practitioner
H 3 R	Histamine-3 receptor
ICF	Informed Consent Form
ICF	Informed Consent Form

MHRA	Medicines and Healthcare products Regulatory Agency
MRI	Magnetic Resonance Imaging
MS IDREC	Medical Sciences Interdivisional Research Ethics Committee
NICE	National Institute for Health and Care Excellence
OHBA	Oxford Centre for Human Brain Activity
PANAS	Positive and Negative Affect Schedule
PDQ	Perceived Deficits Questionnaire
PEACE	Pitolisant effects on affect and cognition exploratory (study)
PFC	Prefrontal Cortex
PHQ-9	Patient Health Questionnaire
PI	Principal Investigator
PILT	Probabilistic Instrumental Learning Task
PIS	Participant Information Sheet
PPI	Personal Protective Equipment
SCID	Structured Clinical Interview for DSM-5
SCID	Structured Clinical Interview for DSM-5
SOP	Standard Operating Procedure
VAS	Visual Analogue Scale
WIN	Wellcome Centre for Integrative Neuroimaging

## Section E. Background and rationale

While strides have been made in characterising the neurochemical basis of human neurocognitive processes through pharmacological investigation of glutamatergic, dopaminergic and serotonergic agents, animal models suggest other neurotransmitter systems play an equally important role in higher cognitive processes and mood regulation. Among these, the monoaminergic histamine-3 receptor (H3R) system, which is expressed only within the human CNS, has demonstrated potential pro-cognitive and mood enhancing effects via antagonist ligands in rodents. These beneficial effects are thought to be mediated by modulation of growth factor expression and hypothalamus-pituitary axis function, respectively.

H3R is highly expressed within fronto-limbic regions including the prefrontal cortex (PFC), hippocampus and striatum. Higher H3R density is associated with lower activity in the dorsolateral PFC during tasks of working memory, in addition to an association with decreased performance. Further, the hippocampus has a high binding affinity for H3R antagonist ligands, where H3R antagonism leads to increased theta oscillatory activity in the region – hippocampal theta oscillations are considered vital for learning and memory processing. Further, the H3R system is considered essential for modulating basal ganglia (including striatal regions) circuitry which is considered vital for modulating response inhibition, decision-making and reward processing. Finally, given the high expression of H3R density in limbic regions, predominantly the hypothalamus, it is suggested that the H3R may play a role in systems which regulate the interface between cognitive and emotional processing.

Recent clinical approval of selective histamine 3 antagonist pitolisant, considered a first-in-class medication by the FDA, has allowed a novel opportunity to explore its direct effects on human cognition and relevant changes in functional connectivity within fronto-limbic regions of high H3R density. Recent positron emission tomography investigation of a single-dose of pitolisant (36mg) in humans demonstrated that it produces high occupancy of H3R throughout key brain regions involved in cognitive and emotional processing.

In this study, we will use a single dose of pitolisant (36mg) to assess its acute effects on cognitive domains of memory (*n*-back tasks, memory encoding fMRI tasks), decision-making (PILT), resting state functional connectivity (resting state fMRI), emotional/non-emotional executive functioning (Go/No-Go task), and emotional social cues processing (FERT). After screening for inclusion eligibility, healthy volunteers will be randomised to receive either a single dose of pitolisant or placebo in a double-blind, randomised design.

Pitolisant (sold as Wakix®) is currently approved and marketed across the US (FDA) and EU (EMA) for the treatment of narcolepsy with or without cataplexy in adults. For this clinical indication, it is recommended that a dose of 4.5mg – 36mg per day is used. Clinical safety data from clinical studies reveals pitolisant to be safe and well-tolerated when used within this dose range in both patients with narcolepsy and healthy volunteers. The most common adverse events reported in trial were nausea (6%), insomnia (6%), and anxiety (5%); many of these side effects are from long-term administration of the drug, and are therefore less likely to present healthy individuals during a single-dose study design.

